1.5 Risks/Benefits

1. Beneficial Findings:

Animal studies have demonstrated that treatment with F-652 reduces ALT/AST levels in serum and TG in liver. Treatment with IL-22 adenovirus also reduces serum ALT and liver/serum TG levels. Activation of pSTAT3 was seen at 1 hr and was undetectable at 3 hrs. IL-22 induced ALT/AST/TG decreases, however, are not seen in STAT3 (hep-/-) mice. IL-22R1 expression was up-regulated in hepatocytes of alcoholic patients and ethanol-fed mice.

2. Potential Risks:

a. Overdose risk

There has been limited human experience with F-652, either at potential clinical doses or with overdose. Treatment of overdose with F-652 should consist of general supportive measures. If the symptom or sign is judged as a severe disease or disorder, treatment will be administered as per standard of care. There is no known specific antidote for overdose with F-652.

b. Warnings, precautions

There are dose-dependent increases in C reactive protein (CRP) and fibrinogen (FIB) following IV dosing with higher doses of F-652 (30 and 45 µg/kg), commencing at 12-24 hours post-dose. FIB reaches a peak at 96-120 hours post-dose; CRP may reach a peak at 48-72 hours post-dose, returning to normal 2 weeks later.

c. Hypersensitivity

The risk of hypersensitivity reactions to F-652 is unknown. If a significant hypersensitivity reaction occurs, no further doses of F-652 will be administered to that patient and appropriate treatment initiated.

d. Laboratory abnormalities

Increased serum CRP and FIB levels may be observed; these increases will be documented.

e. Local reactions at the injection site

Local injection site reactions such as erythema, dry skin and nummular eczema have occurred after the investigational product was administrated by subcutaneous injection. These changes were seen following intravenous administration at the highest dose (45 ug/kg). Local reactions generally occurred 10 to 17 days after administration of F-652, are usually were mild to moderate. Some subjects required treatment with Elocon (mometasone furoate) 0.1% cream, a moderate to strong topical corticosteroid for their skin reactions.

f. Drug interaction

The potential for drug-drug interactions with F-652 is not known.

g. Pregnancy

Adequate contraceptive methods should be used during treatment with F-652.

h. Geriatric use

There has been no geriatric experience to date.

Since no clinical data is available for F-652; any related SAE will be considered as unexpected.

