We define response to the study drug as a decrease in the AST/ALT or serum triglycerides by 30% or more from baseline to Day 42 or Day 56. We will evaluate the patients' response rate for each cohort in phase I. If at the MTD level, the response rate is seen in only 1 of the 3 patients, an additional group of 6 patients will be recruited and treated at the MTD dose level. If efficacy signals can yet not be demonstrated in 2 or more of the 6 patients, the drug will be deemed ineffective. If efficacy signals are demonstrated at the highest safe dose, patients in the final cohort will be administered a third dose (10mcg/kg, 30 mcg/kg, or 45mcg/kg) of the MTD on Day 7 (± 3 days) following the second dose to determine if efficacy can be increased with additional dosing.

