2.2 Study Design/Type

Schedule of Procedures

Safety Assessments	Screening (-72 hrs)	Day 1 (± 1 day)	Day 3 (± 1 day)	Day 7 (± 3 days)	Day 14 (± 3 days)	Day 28 (± 4 days)	Day 42 (± 2 days)	Day 56 ⁶ (± 2 days)
Inclusion/Exclusion Criteria	X	X						
Physical Examination	X			X	X ⁵	X	X	X
Medical/Surgical History	X		X	X	X	X	X	X
Nutritional Assessment	X				X ⁵		X	X
AUDIT and NIAAA Questionnaires	X							
Timeline Followback Questionnaire	X					X	X	X
Vital Signs	X		X		X	X	X	X
Serial Vital Signs		X		X	X ⁵			
Serum Chemistry ^A	X	X	X	X	X	X	X	X
Coagulation ^A	X	X	X	X	X	X	X	X
Hematology ^A	X	X	X	X	X	X	X	X
Serum pregnancy test	X							
Urine pregnancy test		X		X	X ⁵			
Lipid profile, CRP, SAA1, total protein, albumin ^A	X			X	X ⁵	X		
Calculate MELD Score	X	X	X	X	X	X	X	X
Calculate Lille Score				X				
Calculate Maddrey Score	X							
Urinalysis ¹	X							
ECG ²	X			X	X ⁵	X		
Chest X-ray ³	X							
Adverse Events		X	X	X	X	X	X	X
Concomitant Medications	X	X	X	X	X	X	X	X
Study Drug Dosing		X		X	X ⁵			
Pharmacokinetic Sample Collection ⁷		X	X	X	X	X	X	
Immunogenicity Testing ⁸	X				X	X	X	
Biomarkers(blood and urine)	X ⁷			X	X	X	X	X
Confirmation that patient is abstinent from alcohol		X	X	X	X	X	X	X

1. Urinalysis results can be used for Screening if tested within 7 days.
2. ECG results can be used for Screening if tested within 7 days.
3. Chest X-ray results can be used for Screening if tested within 30 days.
4. Day 1, Day 7 and Day 14 labs and testing must be completed prior to dosing.
5. These tests/procedures will occur only on Day 14 if the patient is receiving a 3rd dose at that visit.
6. Day 56 will only occur if the patient received a 3rd dose on Day 14.
7. Biomarkers are optional at Screening.

^AClinical Laboratory Tests

Hematology	Coagulation	Serum Chemistry		Urinalysis	Other
		Liver Function Tests	Other Chemistry		
Complete Blood Count with differential, Platelet count, MCV	PT, INR	AST, ALT, Total Bilirubin, Direct Bilirubin	Sodium, Potassium, Chloride, Bicarbonate, Calcium, Magnesium, Phosphate, Creatinine, BUN, Glucose, Total protein, Albumin, Lipid profile, CRP, SAA1	Specific gravity, pH, Blood, Protein, Glucose, Ketones	β-HCG serum pregnancy test Urine pregnancy test

Blood will be collected for PK sampling per the schedule below:

⁸Pharmacokinetic Sampling Schedule

Study Visit Day					Study Visit Day +0*	Study Visit Day +2*	Study Visit Day +3*	Study Visit Day +4*
					24 hrs	48 hrs	72 hrs	96 hrs

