4.3 Treatment Regimen

F-652 will be administered by slow intravenous infusion over approximately 100 minutes. The study medication is reconstituted as per the protocol in 100 ml of 5% dextrose in water. To monitor, as well as prevent hypersensitivity reactions, the infusion rate will be as follows:

1. 10 ml/hr for 15 minutes
2. 20 ml/hr for 15 minutes
3. 40 ml/hr for 15 minutes
4. 80 ml/hr for 15 minutes
5. 100 ml/hr until infusion complete

That is, the total infusion will be over approximately 100 minutes. Patients will be monitored for 3 hours post-infusion with blood pressure and heart rate monitoring every 30 minutes.

CONFIDENTIAL

This material is the property of the Mayo Clinic. Do not disclose or use except as authorized.

Patients will receive two separate IV infusions separated by 6-10 days (i.e. one infusion on Day 1 and a repeat infusion approximately one week later depending on outpatient scheduling). After information is received regarding the primary end point (safety) at the first dose (10ug/kg), and the 10ug/kg dose determined to be safe, the 2nd cohort of patient will be administered the 30ug/kg dose. Further escalation will follow this scheme. If evaluations demonstrate safety and efficacy signals, patients in the final dose escalation cohort will receive a third dose of the study drug at the maximum tolerated dose on Day 14.

Medications allowed: Corticosteroids, pentoxifylline, antibiotics, acamprosate, and Baclofen, as well as any other medication deemed to be essential for the treatment of the patient will be allowed.

Prohibited medications: Biological agents and any other concomitant investigational agents.

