5.2 Method and Timing

1. MELD score will be calculated at each visit.
2. Lille score will be calculated on Day 7.

CONFIDENTIAL

This material is the property of the Mayo Clinic. Do not disclose or use except as authorized.

3. Triglycerides, CRP and SAA1 will be collected at Screening, Day 7, Day 14 (if dosed) and Day 28.
4. AST and ALT will be collected at Screening, Day 3, Day 7, Day 14, Day 28, Day 35, Day 42 and Day 56 (if applicable).
5. Adverse events will be evaluated at each study visit per the Schedule of Procedures by the study coordinator and reviewed by the investigator

6 *Assessment of Safety*

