Laboratory: Biochemical parameters that are monitored include CRP, liver biochemistry, creatinine, and electrolytes. The study will be **stopped** if two or more patients have **either** A. AST or ALT > 500 U/L **or** B. Lille score > 0.85. The study will also be stopped if more than one patient (that is, two or more) has an adverse event grade 3 or above on the CTCAE scale that is determined to be possibly or likely attributable to study drug as per the study adjudicator. A patient will be **WITHDRAWN** from the dosing phase if Lille scores at any time are > 0.45 (treatment failure).

We recognize that determination of whether worsening of liver biochemical tests is due to the alcoholic hepatitis or study drug induced liver injury (DILI) is very difficult. An AST or ALT increase >500 IU/L would be considered an indication that the patient might have DILI since AST and ALT are typically < 250 U/L in AH. Such an increase of > 500 IU/L would trigger prompt evaluation and consideration of discontinuation of the study drug. A Lille score > 0.85 and an increase in MELD score >10 would also warrant discontinuation of the study drug. Considering how difficult it is to distinguish potential DILI from worsening of the underlying liver disease, we have incorporated an external adjudication of all suspected DILI events. This external adjudication is in addition to the data safety monitoring board (DSMB) which will monitor the entire study. A renowned hepatologist, [name], who is an internationally renowned expert both in the field of alcoholic hepatitis and DILI, has kindly agreed to serve as the external adjudicator for this IL 22 study. He will be contacted on an as needed basis when there is question of symptom causality.

The following parameters will be recorded for the safety evaluation:

- Adverse events
- Vital signs (pulse, heart rate, respiration)
- Physical examinations
- Clinical chemistry, hematology, coagulation, and urinalysis
- ECGs
- Chest X-Ray

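### Fibrinogen rises are to be documented but fibrinogen is in no laboratory list, and the protocol contradicts itself on when CRP is drawn

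*Combined protocol and SAP*

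**What the plan says.** Section 1.5 gives the warning: "There are dose-dependent increases in C reactive protein (CRP) and fibrinogen (FIB) following IV dosing with higher doses of F-652", namely 30 and 45 µg/kg, starting 12–24 h after dosing. It adds the time course: "FIB reaches a peak at 96-120 hours post-dose; CRP may reach a peak at 48-72 hours post-dose, returning to normal 2 weeks later." Under laboratory abnormalities it commits: "Increased serum CRP and FIB levels may be observed; these increases will be documented."

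**Fibrinogen.** It appears in section 1.5 and, as FIB, in the abbreviation list, and nowhere else. The coagulation column of the laboratory table in section 2.2 holds PT and INR. Section 15 also has PT and INR only. The visit lists in section 2.1 name coagulation without adding to it. Section 6.1 says "Biochemical parameters that are monitored include CRP, liver biochemistry, creatinine, and electrolytes", with no fibrinogen.

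**CRP.** Section 5.2 states: "Triglycerides, CRP and SAA1 will be collected at Screening, Day 7, Day 14 (if dosed) and Day 28." The dedicated CRP row of the schedule in section 2.2 and the visit lists in section 2.1 agree. Dosing-day samples are pre-dose: "Day 1, Day 7 and Day 14 labs and testing must be completed prior to dosing." Section 15 keeps CRP and SAA1 under special investigations, apart from serum chemistry. The laboratory table that expands footnote A of the schedule differs. It places CRP and SAA1 within serum chemistry, and the schedule marks serum chemistry at every visit.

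**Dose spacing.** Section 4.3: "Patients will receive two separate IV infusions separated by 6-10 days." For the dose expansion cohort, section 1.6 places the third dose "of the MTD on Day 7 (± 3 days) following the second dose."

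**The concern.** CRP and fibrinogen are the only laboratory abnormalities that section 1.5 attributes to the drug, and it ties them to the two higher doses. Safety is the primary objective and pharmacodynamics a secondary one (section 2), CRP is a named biomarker of IL-22 activity, and section 1.6 makes escalation wait for PK/PD data. A commitment to document a change needs a baseline and at least one timely post-dose value. Fibrinogen has neither. Without a baseline, even an incidental local result could not be read as an increase.

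The earlier evidence does not settle the matter. Section 1.4 reports no laboratory trends or changes at any dose in healthy volunteers, which sits badly with the rises in section 1.5. This trial is the opportunity to learn what happens in alcoholic hepatitis, where section 1.1 notes that coagulation may already be impaired.

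**Working it through.** No sample size, power or error rate is involved, so the plan has no figure to reproduce. The check has two parts: a search of the laboratory lists, and elapsed time from dose to draw.

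**1. Fibrinogen.** None of the four kinds of list names it: the laboratory table and schedule (2.2), the visit lists (2.1), the safety text (6.1) and the analyte list (15). Scheduled measurements: 0 per patient. Planned patients: 9 + 9 = 18. At 30 or 45 µg/kg: (3 + 3) × 2 phases = 12.

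**2. CRP under section 5.2, the CRP row and the visit lists.** Elapsed hours = 24 × (draw day − dose day). The stated CRP peak is 48–72 h.

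| CRP draw | Counted from | Nominal | Range | Nominally in peak? |
|---|---|---|---|---|
| Day 7, pre-dose | Dose 1 | 24 × (7 − 1) = 144 h | 144–240 h under the 6–10 day spacing | No |
| Day 14, pre-dose, third-dose patients only | Dose 2 | 24 × (14 − 7) = 168 h | 96–240 h under the 7 ± 3 day spacing | No |
| Day 28, two-dose patients | Dose 2 | 24 × (28 − 7) = 504 h (21 days) | 14–28 days from visit windows | No |
| Day 28, three-dose patients | Dose 3 | 24 × (28 − 14) = 336 h (14 days) | 7–21 days from visit windows | No |

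The visit windows alone would allow the Day 7 draw at 48–240 h, but the dose spacing in section 4.3 rules out the early part.

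**3. Is a rise still visible?** Section 1.5 does not say whether its 2 weeks run from the dose or from the peak. From the dose, normal is reached at 336 h. From the peak, it is reached at 48 + 336 = 384 h to 72 + 336 = 408 h, about 16–17 days. The Day 7 draw (144–240 h) comes before either, so a rise after dose 1 can be detected past its peak. The nominal Day 28 draw in a two-dose patient (504 h) comes after both. Only the early edge of its window (14 days) could catch a tail.

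**4. CRP if the laboratory table governs.** Day 3 is 24 × (3 − 1) = 48 h after a Day 1 dose (24–72 h with the ±1 day visit window), at the start of the stated peak. Day 14 then gives every patient a value nominally 168 h after dose 2, before the return to normal. No chemistry visit falls nominally in the peak after a later dose: the next one is at 168 h after dose 2 and at 336 h after dose 3.

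**The case against.** The strongest reply concerns CRP. Section 1.5 undertakes to document increases, not peaks, and a Screening value plus a Day 7 draw can show an increase. That stands. A reader might infer that neither named change can be observed; the documents support this for fibrinogen only.

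Second, the laboratory table brings CRP into the Day 3 panel. A reader might infer that CRP misses its peak after every dose, but after dose 1 that depends on which text governs. The reply does not close the matter, though. Footnote A is also attached to the separate CRP row, so the table may be no more than a list of all analytes, and section 5.2, the visit lists and section 15 keep CRP apart from chemistry. A site working from the visit lists would not draw CRP on Day 3. This is a conflict to resolve, not a settled gap.

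Third, no endpoint, stopping rule or analysis in sections 2.3, 6.1, 6.8 or 7.1 uses fibrinogen. That also stands. A reader might infer that the trial would report no fibrinogen rise, or that an escalation decision would change. Neither follows: an unmeasured analyte gives no data rather than a negative result, and no rule depends on it. The pharmacodynamic objective also does not rest on a CRP peak. SAA and triglycerides are named biomarkers too, although section 5.2 puts them on the same schedule. The decrease in CRP listed in section 2.3 can be assessed from the Screening, Day 7 and Day 28 draws.

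**Conclusion.** The point holds in two parts of different strength.

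- **Fibrinogen: firm.** The commitment in section 1.5 has no measurement behind it in any of the 18 planned patients, including the 12 planned at the doses named in the warning. This depends on no visit window and no choice between tables. The count of 12 assumes three patients per cohort, with no extra patients and escalation reaching 45 µg/kg in both phases.
- **CRP: an internal conflict with consequences.** Under section 5.2, the CRP row and the visit lists, no nominal draw falls in the 48–72 h peak, and the rise after dose 2 in two-dose patients is probably missed. Under the laboratory table, the peak after dose 1 is sampled at Day 3 and every patient has a Day 14 value. On both readings a rise after dose 1 is detectable at Day 7.

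The timing rests on nominal visit days and on the time course in section 1.5, taken as given. The defect affects a stated safety commitment and the pharmacodynamic record. It does not affect the primary endpoint or any stopping rule. It should be corrected.

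**What to change.** 1. Add fibrinogen to the coagulation panel in section 2.2 and to section 15, at Screening and at each visit that already draws PT/INR.
2. Reconcile section 5.2, the CRP row, the visit lists and section 15 with the laboratory table, so that CRP and SAA1 are drawn on Day 3 and on Day 14 in all patients. State explicitly whether they are also due at the other chemistry visits.
3. Optionally, run CRP and fibrinogen on the 48, 72 and 96 h pharmacokinetic draws already listed after the Day 7 dose. These cover the CRP peak and the start of the fibrinogen peak (96–120 h). The documents do not give tube type or volume, so feasibility must be confirmed first.

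Step 1 makes a fibrinogen rise visible but not its peak after dose 1, because the nominal visits at 48 h and 144 h fall either side of 96–120 h.

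Cost: an amendment to the laboratory table and visit lists, plus assays. A two-dose patient has 7 coagulation draws (Screening, Days 1, 3, 7, 14, 28 and 42), so 7 × 18 = 126 fibrinogen assays, plus one at Day 56 for each third-dose patient. Measured against section 5.2, CRP and SAA1 each gain at most 2 × 18 = 36 assays. The documents give no prices, but these are routine additions at visits where blood is already taken. No visit is added and no dose, escalation or stopping rule changes.

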This material is the property of the Mayo Clinic. Do not disclose or use except as authorized.

A liver biopsy is required for confirmation of ASH for all patients with clinically-diagnosed AH who have one or more of the following possible confounding factors:

1. Possible ischemic hepatitis (e.g., severe upper gastrointestinal bleed, hypotension, or cocaine use within the prior 7 days)
2. Possible drug-induced liver injury/jaundice
3. Recent sepsis (i.e., infection requiring antibiotics within the prior 7 days)
4. Uncertain alcohol assessment (e.g., patient denies recent/excessive alcohol use)
5. Atypical laboratory tests (e.g., AST < 40 IU/mL or >500 IU/mL, AST/ALT ratio <1.5).

Alcoholic hepatitis usually persists and progresses to cirrhosis if heavy alcohol use continues. If alcohol use ceases, alcoholic hepatitis resolves slowly over weeks to months, sometimes without permanent sequelae but often with residual cirrhosis.

Corticosteroids have been utilized as a standard of care in various treatment guidelines for patients with severe alcoholic hepatitis, as manifested by hepatic encephalopathy or a Maddrey Discriminant Function > 32. However, their applicability in clinical practice is limited in “special populations” of patients who have contraindications to corticosteroids and/or fall into subcategories of patients who were not included in the corticosteroid treatment trials that formed the basis of these treatment guidelines. These special populations are substantial and include patients with renal failure, infection, GI bleed, pancreatitis, and viral hepatitis. Pentoxifylline has also been used because of its safety, but several well-conducted studies have not supported the efficacy of pentoxifylline for the treatment of severe AH. A recent study has questioned the efficacy of both prednisone and pentoxifylline in the treatment of alcoholic hepatitis. Mortality at 6 months was similar in patients on either prednisone, pentoxifylline, or both as compared with placebo. Therefore, there is a need for investigational therapies.

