1.9 Power Calculation

As the primary outcome is observational, we have powered this study based upon the efficacy outcome, which is defined as a biochemical signal for success if AST/ALT is reduced by at least 30% on treatment. With no treatment, approximately 15-20% of patients reach this outcome following study drug treatment. We anticipate that a minimum of 50% will achieve this outcome. Using a conservative 2-sided assessment of superiority (50% with outcome vs. 20%), we will require 22 subjects to reach 80% statistical power.

For our efficacy outcome of AST/ALT, our primary analysis will assess a binary outcome of at least 30% reduction when on treatment. We will evaluate this with a 95% confidence interval of the percentage of subjects who have at least 30% reduction in AST/ALT on treatment, using an exact binary confidence interval. As a secondary analysis, we will use

CONFIDENTIAL

This material is the property of the Mayo Clinic. Do not disclose or use except as authorized.

robust linear regression with the change in AST/ALT at follow-up as compared to baseline as the outcome variable and baseline AST/ALT as the predictor. We will pair this analysis with a Bland-Altman plot. The goal of the secondary analysis is to assess the degree to which the reduction in AST/ALT attributable to treatment changes according to the subject's baseline AST/ALT. We will use 2-sides 5% type I error rate throughout.

2 *Study Objectives*

Primary:

- Assess the safety and tolerability and find the MTD of F-652 in patients with alcoholic hepatitis as determined by:
 - a. Absence of unexpected serious adverse events and,
 - b. Absence of worsening of alcoholic hepatitis (as determined by increase in MELD score > 5) up to Day 56 following administration of first dose of study drug.

Secondary:

- Determine the pharmacokinetics (PK) and pharmacodynamics (PD) of F-652 in patients with alcoholic hepatitis.

Additional:

- Assess the efficacy signal of F-652 in patients with alcoholic hepatitis as determined by:
 - a. Clinical: improvement in clinical status
 - b. Biochemical: Improvement in liver biochemistry, MELD and Lille scores at days 7, 28, 42 and 56
 - c. Biomarkers of IL 22 activity (CRP, SAA, triglycerides)

2.1 **Trial Design:**

The following study evaluations will be performed during the course of the Screening period (Day -3 to Day 0):

- Signed informed consent

CONFIDENTIAL

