7.1 Statistical Methods

Primary endpoint (safety): The number and percentage of patients with SAE and increase in MELD score > 5 up to Day 56 following administration of first dose of study drug will be summarized by each dose level. Ninety-five percent confidence interval of the percentage will be calculated too.

Summary of adverse event will also be provided by each dose level.

Secondary endpoint: Pharmacokinetics (PK) and pharmacodynamics (PD) of F-652 in patients with alcoholic hepatitis at the first dose level (10ug/kg) and subsequent dose levels will be determined by the study sponsor using standard pharmacological tools. The total exposure (area under the curve), maximum serum concentration, time at maximum concentration, last measurable serum concentration, time at last measurable concentration, clearance, volume of distribution, elimination half-life, accumulation ratio and dose proportionality will be calculated.

Efficacy signal endpoint: The main efficacy end point is the reduction of AST/ALT or serum triglycerides. If patients show a reduction of AST/ALT or serum triglyceride by 30% at day 42, the drug shows efficacy in this patient. We will calculate the percentage of patients with efficacy (rate) and its 95% confidence interval for each dose level.

We will also use the proportion of patients with 30% change of AST, ALT from baseline to Day 3, Day7, Day14, Day 28, Day 42 and Day 56 as the dependent variable, dose level and baseline AST, ALT and other patients' characteristic at baseline as the covariates to evaluate the change (efficacy) or drug by dose level. A random intercept will be included for accommodating the correlation among the repeated measurement.

Other efficacy endpoints: Paired t-test or signed-rank test will be used to compare the level Lille score. Linear mixed-effect models will be used to analyze the MELD score, triglycerides, CRP, and SAA1 in a similar way to the AST/ALT.

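### Section 1.6 allows response to be read at Day 56, a visit only three-dose patients have, while section 7.1 reads it at Day 42; used for the third-dose question, the 1.6 definition builds in a timing advantage for three doses

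*Combined protocol and SAP*

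**What the plan says.** Section 1.6 (Dose Expansion cohort) defines response as a "decrease in the AST/ALT or serum triglycerides by 30% or more from baseline to Day 42 or Day 56". It does not say which visit counts for whom, or whether either would do. The same section gives the reason for the third dose: "to determine if efficacy can be increased with additional dosing".

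Section 7.1 sets the main efficacy rule at one visit: "If patients show a reduction of AST/ALT or serum triglyceride by 30% at day 42, the drug shows efficacy in this patient". It reports the rate with a 95% confidence interval for each dose level. It then describes a repeated-measures model of 30% change in AST and ALT at Days 3, 7, 14, 28, 42 and 56. The covariates named are dose level, baseline AST and ALT, and other baseline characteristics, with a random intercept. Neither visit nor number of doses is listed.

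Section 1.9 names no day: "our primary analysis will assess a binary outcome of at least 30% reduction when on treatment".

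The schedule footnote in section 2.2 reads: "Day 56 will only occur if the patient received a 3rd dose on Day 14". On the natural course, section 1.1 says: "If alcohol use ceases, alcoholic hepatitis resolves slowly over weeks to months". Abstinence is checked at every visit from Day 1.

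**The concern.** Under section 1.6 the time at which response is read can depend on how many doses the patient received. A two-dose patient can be read only at Day 42; a three-dose patient can be read at Day 56. There is no control arm to absorb recovery time. In a disease expected to improve with abstinence, a later reading alone can raise the response rate, and that rise could be credited to the third dose.

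A second problem lies in section 7.1. Even with Day 42 as the landmark, a summary by dose level alone puts two-dose and three-dose patients at the same µg/kg on one line, so the contrast that 1.6 wants is not shown. The repeated-measures model takes Day 56 records that come only from three-dose patients, with nothing listed to separate elapsed time from dosing.

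**Working it through.** **The plan's own figure.** Section 1.9 asks for 22 subjects (50% against 20%, two-sided 5%, 80% power). A single-sample formula with the variance at the alternative gives (1.960 + 0.842)² × 0.5 × 0.5 / 0.3² = 21.8, so 22. It reproduces and does not depend on the visit. The plan gives no figure for timing.

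**Clock times, from the visit schedule.** Doses are on Days 1 and 7, and on Day 14 where a third is given.

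| Patient and reading | Time after the Day 42 reading | Days since last dose |
|---|---|---|
| Two doses, Day 42 | 0 | 42 − 7 = 35 |
| Three doses, Day 42 | 0 | 42 − 14 = 28 |
| Three doses, Day 56 | 14 | 56 − 14 = 42 |

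A Day 56 reading is therefore 14 days later from first dose and 7 days later from last dose than a two-dose patient's Day 42 reading.

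**Illustration 1: Day 56 replaces Day 42 (one later look).** Assume a constant recovery hazard from Day 1, no drug effect, and response that persists once reached. With rate r at Day 42, h = −ln(1 − r)/42, and the rate at Day 56 is 1 − exp(−56h) = 1 − (1 − r)^(56/42).

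- r = 15%: 1 − 0.85^1.333 = 19.5%
- r = 20%: 1 − 0.80^1.333 = 25.7%
- r = 35%: 43.7%
- r = 50%: 60.3%

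The 15–20% is section 1.9's untreated rate, for which no day is stated; placing it at Day 42 is an assumption. In a cohort of three, 20% against 25.7% is 0.60 against 0.77 expected responders.

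**Illustration 2: either visit counts (two looks).** Assume the same rate p at both visits and a latent bivariate normal correlation ρ. Then P(response at either) = 2p − P(response at both).

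| ρ | p = 15% | p = 20% |
|---|---|---|
| 0.9 | 19.2% | 25.0% |
| 0.7 | 22.2% | 28.7% |
| 0.5 | 24.2% | 31.3% |

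For p = 20%, the chance of two or more responders among three patients rises from 10.4% to between 15.6% (ρ = 0.9) and 23.2% (ρ = 0.5). These figures apply only if 1.6 is read as allowing either visit.

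**With one common day,** the difference due to time from first dose is zero by construction.

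The documents give no hazard, correlation or variability. Triglycerides are scheduled no later than Day 28 (section 5.2), so any Day 56 effect can act only through AST/ALT.

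**The case against.** The strongest reply is that section 7.1 already fixes the main efficacy rate at Day 42 for every patient. That stands: the rate carries no timing bias. A reader might infer that the trial's efficacy analysis as a whole is biased, and the documents do not support that. The phase I response evaluation in 1.6 is also largely unaffected, because those patients are planned for two doses, have no Day 56 visit, and so are read at Day 42.

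A reader might also infer that the responder is timed three ways, with 1.9 setting a dosing-period landmark. The 1.9 wording follows a statement about untreated patients and plausibly means treated as against untreated; the same section then analyses change at follow-up. It names no day, which is worth repairing, but it does not establish a third landmark.

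A third tempting reading is that three-dose patients get two chances. The Study Summary objectives and the escalation rule in 1.6 use the same pair of days for the end of follow-up, and section 1.8 ties 56 days to the expansion cohort. One look per patient is therefore the more plausible meaning, and the either-visit figures are only conditional.

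Net direction is not settled. Sections 2.4 and 1.6 place the third dose at the end of escalation, in MELD 21–28 patients. Against two-dose patients with MELD 11–20, the difference in severity could offset the timing effect. Recovery depends on abstinence, so relapse before Day 56 could undo a response, whereas the hazard model treats response as permanent. It also starts the recovery clock at Day 1, although the last drink may be up to six weeks before entry.

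Finally, no formal test of three against two doses is planned, efficacy is an additional objective, and the Study Summary leaves detail to a Statistical Analysis Plan. These points limit the importance of the issue. They do not resolve the conflict between 1.6 and 7.1, since the text gives neither section precedence on the third-dose question.

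**Conclusion.** The point holds in conditional form. Sections 1.6 and 7.1 disagree on when response is read, and the later day is available only to three-dose patients. If the 1.6 definition is used to judge whether a third dose adds efficacy, the timing component favours three doses for as long as enzymes are still falling. In the illustration, 20% becomes about 26% as one later look; on the looser either-visit reading it becomes about 25–31% for correlations of 0.9 to 0.5. Both rest on assumptions that the documents neither give nor test. The net bias of the comparison, including MELD stratum, is not established.

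Separately, section 7.1 as written would not display the two-dose and three-dose groups apart at the same dose level, and its repeated-measures model lists no term that separates later visits from additional dosing. This affects the interpretation of an efficacy signal, not the primary safety endpoint. It should be corrected before analysis.

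**What to change.** 1. In section 1.6, replace the two-day definition with Day 42 (±2) AST/ALT as the single responder landmark for all patients, matching 7.1. Name the same day in 1.9.
2. Report Day 56 AST/ALT descriptively, as a later value in three-dose patients.
3. In section 7.1, tabulate response by number of doses within dose level.
4. In the 7.1 repeated-measures model, either add visit and number of doses as terms, or restrict it to visits common to all patients. With at most 18 patients, the restriction asks less of the data.

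The cost is wording in three sections, plus one table and one model specification. Day 42 AST/ALT is already scheduled for everyone, so no visit, sample or patient is added and dosing is untouched.

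The downside should be stated in the plan. A common Day 42 equalises time from first dose, but it reads three-dose patients about 28 days after their last dose, against about 35 days for two-dose patients. No single visit in the schedule aligns both clocks. The triglyceride part of the definition, which has no scheduled sample at Day 42 or Day 56, is a separate matter that this change does not resolve.
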